1.2.4.2 Experience in Hepatitis/HCC

Tremelimumab has recently been shown to be safe in a study in HCC. Twenty-one patients with HCV-related HCC were treated with Tremelimumab intravenously at a dose of 15 mg/kg every 90 days for two cycles. Toxicity was manageable with reported treatment-related adverse events among 80% of patients. Grade 3 or higher adverse events included 1 case of pruritus, 1 case of purpura, and 5 cases of elevated transaminases. There was preliminary evidence of efficacy. In an intention-to-treat analysis, investigators observed a median overall survival of 7.5 months and time to progression of 6.4 months as well as a reduction of hepatitis C virus (HCV) in the patients' blood, which was also accompanied with objective enhancements of antiviral immunity. A significant and progressive decline in serum HCV viral load was observed (median values: baseline 3.78×10^5 copies/ml vs. day 120 3.02×10^4 copies/ml, $P = .02$; vs. day 210 1.69×10^3 copies/ml, $P = .04$).

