- 2.1.2.13 HIV-positive patients receiving anti-retroviral therapy are excluded from this study due to the possibility of pharmacokinetic interactions between antiretroviral medications and Tremelimumab. HIV positive patients not receiving antiretroviral therapy are excluded due to the possibility that Tremelimumab may worsen their condition and the likelihood that the underlying condition may obscure the attribution of adverse events.
- 2.1.2.14 History of hypersensitivity reaction to human or mouse antibody products.
- 2.1.2.15 Pregnancy and breast feeding are exclusion factors. The effects of Tremelimumab on the developing human fetus are unknown. Enrolled patients must agree to use adequate contraception (hormonal or barrier method of birth control; abstinence) prior to study entry, the duration of study participation and 3 months after the end of the treatment. Should a woman become pregnant or suspect she is pregnant while she or her partner is participating in this study, she should inform her treating physician immediately.
- 2.1.2.16 Patients with unhealed surgical wounds for more than 30 days.
- 2.1.3 Re-Induction Criteria (if applicable)
 - 2.1.3.1 Subjects must have entered the Maintenance Phase and are under ongoing maintenance treatment
 - or** Subjects who stopped maintenance treatment because of a CR
 - or** Subjects with an initial PR or CR or at least 3 months of SD on tumor assessment
 - and** who subsequently have a confirmed and documented disease progression (per immune-related RECIST criteria).
 - 2.1.3.2 Patients are excluded from re-induction if they have experienced any related Dose-limiting toxicities as described in Section 3.6, delayed dosing beyond 35 days due to Tremelimumab-related AEs, or have been taken off treatment due to toxicity as described in Section 3.8.3.

2.1.3.3 Patients who have progressed on initial therapy will not be considered for re-induction treatment.

2.1.3.4 Tremelimumab Dose: Patients will be treated at the same dose of Tremelimumab as they previously received. For patients on Dose Level 1 who had already satisfied criteria for escalation to 10mg/kg they will be re-treated at 10mg/kg.

2.1.3.5 The patient must – at the time of re-induction – satisfy all the eligibility criteria as set out in Sections **2.1.1** & **2.1.2**.

2.1.3.6 The patient must be discussed at GI Tumor Board, NCI and suitability for the interventional procedure (TACE or RFA) re-affirmed.

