Eligible patients will follow the same treatment criteria, evaluation plan and schedule as was previously described for the main part of the study, and doses may be delayed or modified as described in Section **3.8**. There will be no limit to the number of additional re-inductions a patient may receive if the same efficacy and safety criteria described above are met, until intolerable toxicity or progressive disease necessitates ending the re-induction phase.

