3.9 DOSING DELAYS

The following broad guidelines for dose delays apply to both of the planned dosages of Tremelimumab and are dependent on the clinical and laboratory assessment on the day of dosing. No dose reductions will be employed. Patients will either proceed or forgo treatment. Dosing may be delayed up to 14 days to allow recovery from treatment-related toxicity. For specific immune-mediated adverse reactions see Section 3.8.3 which will take precedence over this broad management guideline.

Condition	Management
Onset of any toxicity	Rule out alternative etiology In case of doubt, investigator should consult with study medical monitor promptly
NCI CTCAE Grade 1	Provide symptomatic treatment Possible topical steroids if applicable
NCI CTCAE Grade 2	Provide symptomatic treatment In the case of an immune-mediated adverse event do not give scheduled dose; dosing may be resumed once symptoms are resolved. Consider oral or IV steroids at the onset of symptoms. Taper steroid if symptoms improve.
NCI CTCAE Grade 3	Start high-dose IV steroids at the onset of the symptoms Provide symptomatic treatment
NCI CTCAE Grade 4	Start high-dose IV steroids at the onset of the symptoms Provide symptomatic treatment Permanent discontinuation ^a of Tremelimumab for all NCI CTCAE Grade 4 events (unless specific exemption stated elsewhere in protocol)
Steroid refractory toxicity (no improvement after 5 days on high-dose IV steroids) or relapse after reducing high-dose steroids	Continue symptomatic treatment and steroids Possible infliximab ^b 5 mg/kg IV for GI toxicities unless contraindicated [consult with GI specialist]. Caution: rule out bowel perforation and refer to label before using infliximab For subjects with increased AST/ALT, or total bilirubin levels, consider mycophenolate mofetil

ALT = alanine transaminase; AST = aspartate transaminase; GI = gastrointestinal; IV = intravenous; NCI CTCAE = National Cancer Institute Common Terminology Criteria for Adverse Events.

a Subjects will not receive any subsequent dose, but will remain on study and follow the other procedures required from the study (e.g., follow-up procedures, disease assessment scans, blood sample collections).

b Use will result in discontinuation of treatment.

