3.9.1.2 Grade 3 Hematologic or Non-Hematologic Toxicity

Hold Tremelimumab and re-evaluate until toxicity improves to \leq grade 1 or pre-treatment baseline. Treatment will be discontinued in patients who experience grade 3 non-hematologic toxicities felt to be drug-related.

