3.9.2 Toxicities Mandating Permanent Discontinuation of Tremelimumab

As per the Investigator's brochure the following criteria will result in permanent discontinuation of tremelimumab.

Condition	Action
CTCAE Grade ≥ 3 related diarrhea or colitis	Permanent discontinuation of tremelimumab for all listed conditions
AST or ALT $> 8 \times$ ULN or total bilirubin $> 5 \times$ ULN	
CTCAE Grade ≥ 3 hypersensitivity reaction or infusion reaction; Recurrent/persistent CTCAE Grade 2 hypersensitivity	
CTCAE Grade ≥ 3 endocrine disorders, if symptomatic and not controlled with hormone replacement therapy. (Tremelimumab may be dosed for CTCAE Grade ≤ 3 endocrine disorders, if asymptomatic and controlled with hormone replacement therapy.)	
CTCAE Grade 4 rash or other skin disorders (with the exception of vitiligo, which may be dosed regardless of severity)	
Any other CTCAE Grade ≥ 3 events thought to be drug-related	
Any CTCAE Grade ≥ 3 laboratory abnormalities thought to be drug-related	
Patient receives infliximab or any other TNF- α inhibitor	
2 consecutive doses missed due to on-going related toxicities	
Patient begins new investigational therapy, chemotherapy, cytokine therapy, or immunotherapy (including vaccines)	
Patient becomes pregnant	

ALT Alanine transaminase; AST Aspartate aminotransferase; CTCAE Common Terminology Criteria for Adverse Events; TNF Tumor necrosis factor; ULN Upper limit of the normal range.

[figure not shown]

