3.9.3.1 Gastrointestinal

3.9.3.2 Liver (Immune-mediated hepatitis)

Tremelimumab can result in severe and fatal inflammation of the liver most commonly manifested as elevation of transaminases and hyperbilirubinemia. Liver enzymes and liver function tests (hepatic transaminase and bilirubin levels) will be evaluated and patients assessed for signs and symptoms of hepatitis before each dose of Tremelimumab.

In patients who experience AST or ALT > 5.0 ULN and/or baseline or total bilirubin > 3.0 ULN liver biopsy should be considered as per standard of care investigation for autoimmune hepatitis.

Symptoms	Immediate action	Subsequent management
Moderate • AST or ALT >2.5 to 5.0 ULN and/or baseline (if this was abnormal). • Total bilirubin >1.5 to 3.0 ULN	Withhold Tremelimumab • Rule out infectious or malignant causes • Increase frequency of liver function test monitoring until resolution	Symptoms resolve: Resume Tremelimumab if liver function tests are 2.5 ULN or return to baseline and bilirubin level is 1.5 ULN or returns to baseline IF AST OR ALT CONTINUES TO

		ELEVATE TO >5.0 ULN OR TOTAL BILIRUBIN >3.0 ULN, See management for ‘severe’
--	--	---

Symptoms	Immediate action	Subsequent management
Severe 
 • AST or ALT > 5.0 ULN and/or • Total bilirubin > 3.0 ULN 	Hold Tremelimumab and re-evaluate until toxicity improves to \leq grade 1 or pre-treatment baseline. Treatment will be discontinued in patients who experience grade 3 non-hematologic toxicities that do not resolve to grade 1 or baseline within 4 weeks. 
 • Increase frequency of liver function test monitoring until resolution • Administer systemic corticosteroid of 1 to 2 mg/kg/day of prednisone or equivalent. Consider liver biopsy as per standard of care investigation for autoimmune hepatitis 	Symptoms resolve: When liver function tests show sustained improvement or return to baseline, initiate corticosteroid tapering and continue to taper over 1 month Consider alternative immunosuppressive therapy Symptoms Ongoing >1 week: Consider alternative immunosuppressive therapy

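### For liver test elevations, 3.9.2 requires a permanent stop where the Severe row of 3.9.3.2 says hold, and nothing says which rule prevails

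*Combined protocol and SAP*

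**What the plan says.** Four parts of Section 3.9 bear on a drug-related liver test elevation.

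- **3.9.1.2 (general guideline).** After an instruction to hold and re-evaluate, it says: "Treatment will be discontinued in patients who experience grade 3 non-hematologic toxicities felt to be drug-related". No exception is given.
- **3.9.2 (mandatory discontinuation, attributed to the Investigator's brochure).** One row lists AST or ALT above 8 x ULN or total bilirubin above 5 x ULN. A separate row lists any CTCAE Grade 3 or higher "laboratory abnormalities thought to be drug-related". The same table allows dosing for Grade 3 or lower "endocrine disorders, if asymptomatic and controlled with hormone replacement therapy".
- **3.9.3 and 3.9.3.2 (specific immune-mediated reactions, liver).** The opening of 3.9.3 says tremelimumab will be discontinued for severe immune-mediated reactions. The Severe liver row covers AST or ALT above 5.0 ULN and/or total bilirubin above 3.0 ULN, with no upper limit. It says to hold until Grade 1 or baseline, and to discontinue for Grade 3 non-hematologic "toxicities that do not resolve to grade 1 or baseline within 4 weeks".
- **3.9 (precedence).** "For specific immune-mediated adverse reactions see Section 3.8.3 which will take precedence over this broad management guideline". Section 3.8 ends at 3.8.2, so there is no 3.8.3.

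The dead reference recurs in the re-induction criteria. Section 2.1.3.2 excludes patients who "have been taken off treatment due to toxicity as described in Section 3.8.3".

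**The concern.** A stopping rule for toxicity should give one answer for one laboratory result. Here a single drug-related liver result can fall under a rule that ends treatment for good and under another that only pauses it. The sentence that ought to settle the order points to a missing section and does not mention 3.9.2. Two investigators could treat the same result differently, each with the protocol's text in support.

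Liver tests are where this matters most in this population. Patients may enter with ALT or AST up to 5 x ULN (2.1.1.8), which is the edge of the Severe row. Section 3.9.3.2 itself says the drug can cause severe and fatal liver inflammation. The answer also affects later eligibility, because exclusion from re-induction depends partly on having been taken off treatment for toxicity.

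**Working it through.** The plan states no figure to reproduce. The check sets the rules side by side.

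**Inputs.** From 3.9.2: stop if AST/ALT > 8 x ULN, if bilirubin > 5 x ULN, or for any drug-related laboratory abnormality of Grade 3 or higher. From the Severe row of 3.9.3.2: hold if AST/ALT > 5 x ULN and/or bilirubin > 3 x ULN; discontinue a Grade 3 toxicity not resolved within 4 weeks.

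**Assumption.** The documents do not reproduce the CTCAE cut-offs. The cases below are taken to be drug-related and Grade 3.

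**Step 1: apply both rules to the same patient.**

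| Case | 3.9.2 | 3.9.3.2, Severe row | Same outcome? |
|---|---|---|---|
| ALT 6 x ULN, baseline at 3 weeks | Liver row not met (6 < 8); the laboratory row stops if it covers liver tests | Met (6 > 5): hold; 3 < 4 weeks, so no discontinuation | Only if the laboratory row does not cover liver tests |
| ALT 9 x ULN, baseline at 3 weeks | Stop (9 > 8) | Met (9 > 5): hold; 3 < 4 weeks, so no discontinuation | No |
| ALT 9 x ULN, unresolved after 4 weeks | Stop | Hold, then discontinue | Yes in the end |
| Bilirubin 4 x ULN, baseline at 3 weeks | Liver row not met (4 < 5); the laboratory row stops if it covers liver tests | Met (4 > 3): hold; no discontinuation | Only if the laboratory row does not cover liver tests |
| Bilirubin 5.1 x ULN, baseline at 3 weeks | Stop (5.1 > 5) | Met (5.1 > 3): hold; no discontinuation | No |

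Above 8 x ULN (AST/ALT) or 5 x ULN (bilirubin), both sections apply on their own numbers. From above 5 to 8 x ULN, or above 3 to 5 x ULN, they conflict only if the Grade 3 laboratory row of 3.9.2 is meant to include liver tests.

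**Step 2: look for an order of precedence.** Section 3.9.3 carries the title on specific immune-mediated reactions, so the citation of 3.8.3 evidently means 3.9.3. Corrected, the clause places 3.9.3 above a broad management guideline. That fits the grade table in 3.9 and the general guidelines in 3.9.1. It does not name 3.9.2, whose list is framed as mandatory.

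**Step 3: check 3.9.3 against itself.** Its opening discontinues the drug for severe immune-mediated reactions, yet its liver row labeled Severe holds the drug. Fixing the order between 3.9.2 and 3.9.3 does not remove this.

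**Step 4: the endocrine rule.** Take a drug-related Grade 3 endocrine disorder that is asymptomatic and controlled on hormone replacement. Read alone, 3.9.1.2 discontinues. But 3.9.2 allows dosing, 3.9.3.5 resumes once the patient is stable, and the paragraph after the table in 3.9 lets patients with adrenal insufficiency take daily prednisone while on treatment. With the precedence clause corrected, 3.9.3.5 outranks 3.9.1.2. What remains is an inconsistency of wording.

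**The case against.** The best defense is a tiered reading: hold from above 5 to 8 x ULN, stop above 8, and likewise for bilirubin at 3 and 5. A list headed as mandating permanent discontinuation works naturally as a cap on a hold rule, and both texts can be obeyed by holding at once and then stopping. This is sensible and probably what was meant. But it is not written down, the Severe row has no ceiling, and the Grade 3 laboratory row would still collide with the hold inside the lower band if it covers liver tests.

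Three further objections narrow the point. First, the Severe row contains no instruction to resume; the Moderate row does. Restarting after recovery is implied by the 4-week sentence, not stated. Second, the opening of 3.9.3 already points toward discontinuation in severe cases. That weakens any picture of 3.9.3 as purely a hold rule, but it adds an internal inconsistency. Third, the 4-week allowance names Grade 3 only, and the table in 3.9 stops treatment for Grade 4 events unless the protocol exempts them. So the absence of a ceiling does not carry the allowance into Grade 4.

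A reader might also infer that 3.9.1.2 wrongly withdraws drug from patients with controlled endocrine disorders. The documents do not support giving that much weight: three other provisions agree on dosing, and the corrected precedence clause favors the specific endocrine section.

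**Conclusion.** The liver rules conflict as written. The conflict is definite for a drug-related Grade 3 result above 8 x ULN (AST/ALT) or 5 x ULN (bilirubin) that recovers within 4 weeks. It is conditional in the bands just below. This assumes that some values above those limits are Grade 3 and that the 4-week sentence is read in its ordinary sense.

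Three stronger conclusions are tempting and should not be drawn.

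- A reader might infer that the protocol tells investigators to restart patients who have passed a mandatory stop. It does not. That result needs both an implied resumption and a reading of the precedence clause that puts 3.9.3 above 3.9.2, which is the less natural one.
- A reader might take the earlier tremelimumab study in HCC, with "5 cases of elevated transaminases" at Grade 3 or higher among 21 patients, as the frequency of the conflict. Section 1.2.4.2 gives no count above 8 x ULN and no recovery times, and that study used 15 mg/kg every 90 days in HCV-related disease. The documents support no rate.
- A reader might infer that the three-dose feasibility result or the efficacy calculations are undermined. Section 8.1 records feasibility as already determined, and the power figures for stable disease at 6 months do not use these rules. No statistical result changes.

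This is a modest but worthwhile safety clarification. Which liver rule is clinically right is for the sponsor.

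**What to change.** 1. In 3.9, change the reference from 3.8.3 to 3.9.3. Add that a mandatory discontinuation in 3.9.2 prevails over the hold provisions of 3.9.3, so that the Severe liver row's hold applies at most up to 8 x ULN for AST/ALT or 5 x ULN for bilirubin.
2. State whether the Grade 3 laboratory row of 3.9.2 covers AST/ALT above 5 to 8 x ULN and bilirubin above 3 to 5 x ULN. Align the opening of 3.9.3 and the Severe row of 3.9.3.2 with that choice, including whether a patient who recovers may resume.
3. As a minor consistency edit, add to 3.9.1.2 an exception for endocrine disorders that 3.9.2 allows to be dosed.
4. In 2.1.3.2, point the re-induction exclusion to both 3.9.2 and 3.9.3. Replacing 3.8.3 with 3.9.3 alone would leave out the mandatory-discontinuation list.

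Other outdated section numbers are clerical and can be corrected in the same pass, for example the re-induction text "doses may be delayed or modified as described in Section" 3.8, which should read 3.9.

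The cost is wording in one amendment: no new data, visits or patients.

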3.9.1.3 Grade 4 Non-Hematologic Toxicity

Patients with clinical treatment-related grade 4 non-hematologic toxicity (except pulmonary embolism without significant hypoxia and hemodynamic instability) will be taken off treatment permanently. Unacceptable toxicities that have not resolved at time of "off treatment" must be followed until stabilization or resolution, at which time they will continue in follow up for survival.

3.9.2 Toxicities Mandating Permanent Discontinuation of Tremelimumab

As per the Investigator's brochure the following criteria will result in permanent discontinuation of tremelimumab.

Condition	Action
CTCAE Grade ≥ 3 related diarrhea or colitis	Permanent discontinuation of tremelimumab for all listed conditions
AST or ALT $> 8 \times$ ULN or total bilirubin $> 5 \times$ ULN	
CTCAE Grade ≥ 3 hypersensitivity reaction or infusion reaction; Recurrent/persistent CTCAE Grade 2 hypersensitivity	
CTCAE Grade ≥ 3 endocrine disorders, if symptomatic and not controlled with hormone replacement therapy. (Tremelimumab may be dosed for CTCAE Grade ≤ 3 endocrine disorders, if asymptomatic and controlled with hormone replacement therapy.)	
CTCAE Grade 4 rash or other skin disorders (with the exception of vitiligo, which may be dosed regardless of severity)	
Any other CTCAE Grade ≥ 3 events thought to be drug-related	
Any CTCAE Grade ≥ 3 laboratory abnormalities thought to be drug-related	
Patient receives infliximab or any other TNF- α inhibitor	
2 consecutive doses missed due to on-going related toxicities	
Patient begins new investigational therapy, chemotherapy, cytokine therapy, or immunotherapy (including vaccines)	
Patient becomes pregnant	

ALT Alanine transaminase; AST Aspartate aminotransferase; CTCAE Common Terminology Criteria for Adverse Events; TNF Tumor necrosis factor; ULN Upper limit of the normal range.

[figure not shown]
3.9.3 Specific immune-mediated adverse reactions

Tremelimumab can result in severe and fatal immune-mediated adverse reactions due to T-cell activation and proliferation. These immune-mediated reactions may involve any organ system, however, the most common severe immune-mediated adverse reactions are enterocolitis, hepatitis, dermatitis (including toxic epidermal necrolysis), neuropathy, and endocrinopathy. The majority of these immune-mediated reactions initially manifest during treatment, however, a minority may occur weeks to months after discontinuation of Tremelimumab. Tremelimumab will be discontinued and systemic high-dose corticosteroid therapy initiated for severe immune-mediated reactions.

Patients will be assessed for signs and symptoms of enterocolitis, dermatitis, neuropathy and endocrinopathy and evaluate clinical chemistries including liver function tests and thyroid function tests at baseline and before each dose.

The following are anticipated immune-mediated adverse reactions for which specific guidance and management is outlined below.

3.9.3.1 Gastrointestinal

3.9.3.2 Liver (Immune-mediated hepatitis)

Tremelimumab can result in severe and fatal inflammation of the liver most commonly manifested as elevation of transaminases and hyperbilirubinemia. Liver enzymes and liver function tests (hepatic transaminase and bilirubin levels) will be evaluated and patients assessed for signs and symptoms of hepatitis before each dose of Tremelimumab.

In patients who experience AST or ALT > 5.0 ULN and/or baseline or total bilirubin > 3.0 ULN liver biopsy should be considered as per standard of care investigation for autoimmune hepatitis.

Symptoms	Immediate action	Subsequent management
Moderate • AST or ALT >2.5 to 5.0 ULN and/or baseline (if this was abnormal). • Total bilirubin >1.5 to 3.0 ULN	Withhold Tremelimumab • Rule out infectious or malignant causes • Increase frequency of liver function test monitoring until resolution	Symptoms resolve: Resume Tremelimumab if liver function tests are 2.5 ULN or return to baseline and bilirubin level is 1.5 ULN or returns to baseline IF AST OR ALT CONTINUES TO

		ELEVATE TO >5.0 ULN OR TOTAL BILIRUBIN >3.0 ULN, See management for ‘severe’
--	--	---

Symptoms	Immediate action	Subsequent management
Severe 
 • AST or ALT > 5.0 ULN and/or • Total bilirubin > 3.0 ULN 	Hold Tremelimumab and re-evaluate until toxicity improves to \leq grade 1 or pre-treatment baseline. Treatment will be discontinued in patients who experience grade 3 non-hematologic toxicities that do not resolve to grade 1 or baseline within 4 weeks. 
 • Increase frequency of liver function test monitoring until resolution • Administer systemic corticosteroid of 1 to 2 mg/kg/day of prednisone or equivalent. Consider liver biopsy as per standard of care investigation for autoimmune hepatitis 	Symptoms resolve: When liver function tests show sustained improvement or return to baseline, initiate corticosteroid tapering and continue to taper over 1 month Consider alternative immunosuppressive therapy Symptoms Ongoing >1 week: Consider alternative immunosuppressive therapy

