3.12 CRITERIA FOR REMOVAL FROM PROTOCOL THERAPY AND OFF STUDY CRITERIA

3.12.1 Criteria for removal from protocol therapy

Prior to removal from the study, effort must be made to have all subjects complete a safety visit approximately 30 days following the last dose of study therapy

In the absence of treatment delays due to adverse events, treatment may continue until one of the following criteria applies:

- Disease progression (per immune-related response criteria)
- Completion of 2 years' protocol therapy with tremelimumab
- Intercurrent illness that prevents further administration of treatment
- Unacceptable adverse event(s)
- Participant requests to be withdrawn from active therapy
- Investigator discretion
- Positive pregnancy test
- Delayed recovery from toxicity that prevents re-treatment in ≤ 28 days of scheduled therapy
- Completed end of treatment safety visit

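### The severe-hepatitis row of 3.9.3.2 holds tremelimumab with no upper limit, inconsistent with the stopping rules in 3.9.2, 3.9.1.2 and the 3.9.3 lead-in

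*Combined protocol and SAP*

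**What the plan says.** Five places in the protocol bear on a patient with markedly raised liver values.

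- **3.9.3.2, severe row.** It is entered at AST or ALT above 5 x ULN and/or total bilirubin above 3 x ULN, with no upper bound. The drug is held until toxicity is back to Grade 1 or lower, or to the pre-treatment baseline. The only stop is: "Treatment will be discontinued in patients who experience grade 3 non-hematologic toxicities that do not resolve to grade 1 or baseline within 4 weeks".
- **3.9.2.** Citing the Investigator's brochure, it says that "the following criteria will result in permanent discontinuation of tremelimumab". The list includes "AST or ALT $> 8 \times$ ULN or total bilirubin $> 5 \times$ ULN" and, separately, any Grade 3 or higher "laboratory abnormalities thought to be drug-related". Neither entry has a recovery clause. Where an exception is meant, the row says so, as for skin disorders: "with the exception of vitiligo, which may be dosed regardless of severity".
- **3.9.1.2.** Grade 3 non-hematologic toxicity attributed to the drug leads to discontinuation, with no 4-week allowance.
- **3.9.3, opening paragraph.** For severe immune-mediated reactions the drug is to be discontinued and high-dose steroids started.
- **3.9.** For specific immune-mediated reactions, "see Section 3.8.3 which will take precedence over this broad management guideline". The table there stops the drug for Grade 4 events, "unless specific exemption stated elsewhere in protocol".

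**The concern.** Tables such as the one in 3.9.3.2 are consulted on their own, at the point of care. The severe row has no ceiling and does not refer to 3.9.2. Staff using it alone would hold the drug, treat with steroids and wait up to 4 weeks, and would find no stopping instruction for a patient who recovers in that time. Section 3.9.2 stops the same patient for good if AST or ALT passed 8 x ULN or bilirubin passed 5 x ULN.

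The stake is patient safety and equal handling of like cases. Section 3.9.3.2 itself warns that liver inflammation on this drug can be severe and fatal. The event is foreseeable: section 1.2.4.2 reports 5 cases of Grade 3 or higher transaminase elevation in a tremelimumab study of 21 patients with HCC. That study used a different dose and schedule, and the protocol does not say how many cases exceeded 8 x ULN, so it shows relevance and not a rate.

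**Working it through.** There is no figure in the plan to reproduce. The check sets the rules side by side by level of abnormality.

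| Level | 3.9.3.2 severe row | 3.9.2 | 3.9.1.2 and 3.9.3 lead-in |
|---|---|---|---|
| AST/ALT > 8 x ULN or bilirubin > 5 x ULN | Hold; stop if Grade 3 and unresolved at 4 weeks | Permanent stop, no recovery clause | Discontinue if Grade 3 and drug-related, or if a severe immune-mediated reaction |
| AST/ALT > 5 to 8 x ULN or bilirubin > 3 to 5 x ULN, Grade 3 or higher, thought drug-related | Same as above | Permanent stop (laboratory catch-all) | Same as above |
| Same values, not thought drug-related | Same as above | No liver entry applies | Neither applies |

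1. **Overlap.** Because 8 > 5 and 5 > 3, every value that meets the 3.9.2 liver limits also lies inside the severe row. Nothing in the row sets those values apart.

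2. **Where the outcomes differ.** In the first two lines of the table the sections part when the patient recovers within 4 weeks. Example: ALT reaches 10 x ULN and is back to baseline after 3 weeks. The row's stopping condition is not met. Under 3.9.2 the stop is mandatory, since 10 > 8.

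3. **Where they do not differ.** In the third line 3.9.2 has no liver rule, and the 4-week condition is the operative one. So that condition still has work to do when 3.9.2 is applied in full. The row is entered on laboratory values before cause is settled (it suggests considering a liver biopsy), so this group is not empty by construction.

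4. **Comparison inside 3.9.3.** The severe skin row (3.9.3.3) and the severe nervous-system row (3.9.3.4) direct permanent discontinuation. The severe liver row directs a hold. It also follows the general Grade 3 rule of 3.9.1.2 closely but replaces the drug-related condition with the 4-week one.

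5. **Precedence.** The clause in 3.9 ranks the specific section above the broad guideline and does not mention 3.9.2. If extended to 3.9.2, it would favour the more permissive liver row. Its reference is also out of date: section 3.8 now ends at 3.8.2, and the immune-mediated guidance is 3.9.3.

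6. **Grade 4.** The row's stopping sentence names Grade 3 only. The Grade 4 stop in the 3.9 table yields to exemptions elsewhere. Section 3.9.1.3 permanently stops clinical, treatment-related Grade 4 non-hematologic toxicity.

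**The case against.** The strongest reply is that no two instructions collide. The severe row never tells anyone to restart. The moderate row of the same table does, whereas the severe row's text for resolved symptoms concerns steroid tapering and other immunosuppression. Holding now and stopping permanently above 8 x ULN can both be obeyed for one patient. To re-dose after ALT of 10 x ULN, staff would have to overlook a section titled as mandatory and the lead-in just above the liver table. The precedence clause, read literally, concerns dose delays and does not reach 3.9.2.

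Most of this stands. A reader might infer that the protocol instructs re-dosing after severe hepatitis. The documents do not support that:

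- Resumption is at most implied by the 4-week condition, and that condition keeps a function for elevations below the 3.9.2 limits that are not thought drug-related.
- The criterion in 3.12.1, "Delayed recovery from toxicity that prevents re-treatment in" 28 days, matches 4 x 7 = 28 days but applies to every toxicity. It does not show that re-dosing above 8 x ULN was intended.
- The permission in 3.9 to resume during a steroid taper once symptoms are Grade 1 or lower is equally general.

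The reply does not remove the inconsistency. Reading 3.9.2 as a cap is sensible, but the protocol does not say so. The lead-in to 3.9.3 and section 3.9.1.2 guard against re-dosing, yet they also contradict the row: they say discontinue where it says hold and see whether the patient recovers.

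**Conclusion.** The point holds as an internal inconsistency in the stopping rules for liver toxicity. It is not an instruction to re-dose, and it should be fixed.

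Its extent is two groups of patients: those above the 3.9.2 liver limits, and those below them whose elevation is Grade 3 or higher and thought drug-related. The second group depends on CTCAE grade boundaries, which the protocol cites but does not reproduce. No patient count can be given, because the documents do not say how many events fall in each group or recover within 4 weeks.

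No endpoint, sample size or analysis changes. Section 8.1 records that the three-dose feasibility evaluation had already ended before Amendment G.

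The conclusion assumes that 3.9.2 is meant to be mandatory, as its title and its citation of the Investigator's brochure indicate.

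**What to change.** 1. In the severe row of 3.9.3.2, state that AST or ALT above 8 x ULN, or total bilirubin above 5 x ULN, means permanent discontinuation under 3.9.2.
2. State in 3.9 that 3.9.2 governs over 3.9.3.
3. Below those limits, let drug-related elevations of Grade 3 or higher follow the 3.9.2 stop, unless the sponsor writes a named exception into 3.9.2 in the style of the vitiligo one. An exception would also need matching text in 3.9.1.2 and the 3.9.3 lead-in, and should say expressly when dosing resumes. Which course to take is a clinical decision for the sponsor and the investigator.
4. State that the 4-week hold rule applies to elevations not thought drug-related.
5. Editorial: change the references to 3.8.3 in sections 3.9 and 2.1.3.2 to 3.9.3.

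The cost is a wording amendment and a notice to staff. No patients, visits or procedures are added.
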